3.1.5 Duration of Subject Participation

The duration of the subject participation will be of a maximum of 68 weeks, (77 weeks in case of extension of titration period) including 4 weeks of screening period, titration period of at least 3 months (maximum duration for 5 months), treatment duration of 26 weeks for efficacy and safety evaluation (weeks 13 through weeks 39) and treatment duration of 26 weeks for immunogenicity evaluation (weeks 40 through weeks 64). In substantiated cases a prolongation of the titration period is allowed up to maximum of 4 to 5 months on a case to case basis which will be considered as extended titration period. The assessment will be similar to the visit 7 (week 12/Day 84) if there is prolongation of the titration period.

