6.4 Treatment Period (Week 14/Day 98 to Week 64/Day 448)

The study treatment period will be for 52 weeks. The subject will receive either EPIAO or EPREX one to three times a week at the end of dialysis session. During the treatment period, the subject will be instructed to visit the study facility one to three times a week on week 14/Day 98, week 15/Day 105, week 16/Day 112, week 20/Day 140, week 24/Day 168, week 28/ Day 196, week 32/Day 224, week 36/Day 252, week 40/Day 280, week 44/Day 308, week 48/Day 336, week 52/Day 364, week 60/Day 420 and week 64/Day 448 following randomization for study assessment.

The following assessments will be performed;

Visit 9: Week 14/Day 98 \pm 2 days

- Demographic data (body weight: post hemodialysis)
- Vital signs
- Physical examination
- Adverse events
- Concomitant medication
- CBC

- Dose adjustment if required as per section 5.1.7

Visit 10: Week 15/Day 105 ± 2 days

- Demographic data (body weight: post hemodialysis)
- Vital signs
- Physical examination
- Adverse events
- Concomitant medication
- CBC
 - Reticulocyte count

Dose adjustment if required as per section 5.1.7

Visit 11: Week 16/Day 112 ± 2 days

- Demographic data (body weight: post hemodialysis)
- Vital signs
- Physical examination
- Adverse events
- Concomitant medication
- CBC
- Iron study
- Immunogenicity testing for anti-EPO antibody
- Dose adjustment if required as per section 5.1.7

Visit 12: Week 20/Day 140 ± 2 days

- Demographic data (body weight: post hemodialysis)
- Vital signs
- Physical examination
- Adverse events
- Concomitant medication
- CBC
- Dose adjustment if required as per section 5.1.7

Visit 13: Week 24 /Day 168± 2 days

- Demographic data (body weight: pre and post hemodialysis)
- Vital signs
- Physical examination

- Adverse events
- Concomitant medication
- CBC
- Iron study
- BUN (pre and post hemodialysis)
- Immunogenicity testing for anti-EPO antibody
- Adequacy of dialysis measurement by Kt/V formula
- Dose adjustment if required as per section 5.1.7

Visit 14: Week 28/Day 196 ± 2 days

- Demographic data (body weight: post hemodialysis)
- Vital signs
- Physical examination
- Adverse events
- Concomitant medication
- CBC
- Dose adjustment if required as per section 5.1.7

Visit 15: Week 32/Day 224 ± 2 days

- Demographic data (body weight: post hemodialysis)
- Vital signs
- Physical examination
- Adverse events
- Concomitant medication
- CBC
- Dose adjustment if required as per section 5.1.7

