6.5 End of Treatment / Study

Visit 23: End of study visit Week 64/ Day 448

- Demographic data (body weight: pre and post hemodialysis)
- Vital signs
- Physical examination
- Adverse events
- Concomitant medication
- Laboratory investigations (haematology, serum chemistry, urinalysis* and iron study and reticulocyte count) (refer Table in Appendix I)
- Chest X ray, ECG
- Serum Pregnancy Test (for all females of childbearing potential)
- Immunogenicity testing for anti-EPO antibody
- BUN (pre-and post Dialysis)
- Adequacy of dialysis measurement by Kt/V formula

*= Urinalysis test will be considered as optional for CKD patients as CKD patients may not be able to provide sufficient urine volume for urinalysis test due to low urine output.

Table 2: Study Visit Plan

S No .	Procedures	Screen ing	Titration period							Extend ed Titrati on period	Baseli ne*	Treatment Period												End of Study		
		V 0 (Day - 31 to Day 0)	V 1 (Wk 1/ Day 1)	V 2 (Wk 2/D ay 14)	V 3 (Wk 4/Da y 28)	V 4 (Wk 6/D ay4 2)	V 5 (Wk 8/Day 56)	V 6 (Wk 10/Da y 70)	V 7 (Wk 12/D ay 84)			V 8 (Day 91/ Week 13)	V 9 (Wk 14/ Day 98)	V 10 (Wk 15/ Day 105)	V 11 (Wk 16/ Day 112)	V 12 (Wk 20/ Day 140)	V 13 (Wk 24/ Day 168)	V 14 (Wk 28/ Day 196)	V 15 (Wk 32/ Day 224)	V 16 (Wk 36/ Day 252)	V 17 (Wk 40/ Day 280)	V 18 (Wk 44/ Day 308)	V 19 (Wk 48/ Day 336)	V 20 (Wk 52/ Day 364)	V 21 (Wk 56/D ay 392)	V 22 (Wk 60/ Day 420)
1	Informed Consent	X																								
2	Demographic Data ¹	X		X	X	X	X	X	X															X	X	
3	Medical History	X																								
4	Menstrual and Reproductive History	X																								
5	Physical/Clinical Examination ²	X		X	X	X	X	X	X															X	X	
6	Vital signs ³	X		X	X	X	X	X	X															X	X	
7	Inclusion & Exclusion Criteria	X																								
8	Eligibility Criteria											X														
9	Concomitant Medication ⁴	X		X	X	X	X	X	X															X	X	
10	Peripheral smear	X			X		X		X																	X
11	Complete Blood Count	X		X	X	X	X	X	X															X	X	
12	Reticulocyte Count	X							X	X																X
13	Renal Function (BUN)	X										X													X	X
14	Iron study	X						X				X												X		X
15	CRP																									X
16	Liver Function Test ⁵																									X
17	Serum Chemistry	X																								X
18	HbA1C	X																								X
19	Urinalysis ⁶	X																								X
20	Serology	X																								X

21	Fecal occult¹⁰ blood test & intact parathyroid hormone	X																						

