9 STATISTICAL METHODS

9.1 Analysis Sets

Three cohorts will be considered for the analysis: The modified intention-to-treat (mITT) cohort, per protocol (PP) and safety cohort. Per-Protocol cohort population will be considered as primary population for analysis of efficacy.

Modified Intention-to-treat Cohort:

All randomized subjects who receive study medication, have a baseline and at least one post-treatment measurement will be included in the MITT Cohort.

Per-protocol Cohort:

All randomized subjects who complete both the baseline visit and end of treatment visit and who have no major protocol violations will be included in the PP population. Subjects with major protocol violations will be excluded from this cohort.

Detailed description of what constitutes a protocol violation will be defined in the SAP.

Safety Cohort:

All subjects who are randomized at baseline visit will be included in the safety analyses for safety endpoints.

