9.2 General Statistical Considerations

Analysis for all efficacy endpoints using the PP population will be the primary approach for analysis. Secondary analysis will be performed using the mITT population. For safety endpoints using the safety cohort will be the primary approach for analysis.

The SAS® package (SAS® Institute Inc., USA, and Version 9.2 or higher) will be used for statistical evaluation.

Descriptive statistics, such as mean, standard deviation, median, minimum and maximum values will be provided for the continuous variables and the number of observations and percentage will be provided for the categorical variables.

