9.4 Efficacy Analyses

9.4.1 Primary Efficacy Analyses

- Mean absolute change in haemoglobin level from baseline to 6 months after treatment with EPIAO/EPREX in parallel groups (g/dl).
- Mean absolute change in weekly epoetin dosage per kg body weight from baseline to 6 months after treatment with EPIAO/EPREX in parallel groups (IU/kg/week).

The ANCOVA will be performed based on the normality of data for mean change between baseline to 6 months of EPIAO and EPREX with center, Hb level and weight as covariates. The 95% confidence intervals will be calculated for the treatment differences and is compared with pre-defined acceptance ranges: ± 0.5 g/dl for haemoglobin.

The ANCOVA will be performed based on the normality of data for mean change in weekly epoetin dosage per kg body weight baseline to 6-month treatment with EPIAO and EPREX with center, Hb level and weight as covariates. The 95% confidence intervals will be calculated for the treatment differences and is compared with pre-defined acceptance ranges: ± 45 IU/kg/week for dosage.

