9.4.2 Secondary Efficacy Analyses

- Proportion of subject's hemoglobin values are within 10 - 12 g/dl for the last 4 weeks of the period for assessment of treatment efficacy and safety (Weeks 32-36)
- Proportion of subjects with any haemoglobin measurement outside the target range during the double-blind treatment period
- Mean hemoglobin and hematocrit levels every 4 weeks within treatment period (52 weeks)
- Mean doses of the study products (IU/kg/week) every 4 weeks throughout the study period (52 weeks)
- Incidence of blood transfusions

The appropriate descriptive statistics or frequency and percentages will be presented for the secondary end point. Other analysis will be carried out as deemed appropriate.

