9.6 Interim Analysis

An interim analysis will be conducted to evaluate the therapeutic equivalence of EPIAO with the standard treatment EPREX after a treatment period of 24 weeks. The analysis will be performed by an independent statistician, who is not involved in the trial conduct other than this interim analysis. The independent statistician will be unblinded and will conduct the analysis using actual treatment assignments. This interim analysis will be conducted after all the randomized patients complete the Visit 16 (Week 36/Day 252). The results of the interim analysis will be communicated to Independent sponsor representative. All other personnel involved in the study will remain blinded. The analysis will be performed in terms of efficacy, safety and immunogenicity between the treatment arms as per the final analysis stated in section 9.

The sponsor of the study wishes to use the data from the interim analysis to plan for registration of EPIAO in other countries where it is yet to be marketed. An interim report will be used to meet the requirement for local registration. A complete analysis will be conducted at the end of the treatment period.

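### The primary per-protocol set for two 6-month co-primary endpoints requires a visit that the protocol places at Week 64, so it excludes subjects for later events and cannot be fully formed at the Week 36 analysis

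*Protocol*

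**What the plan says.** Section 9.1 names the PP cohort as the primary population for efficacy and admits "All randomized subjects who complete both the baseline visit and end of treatment visit and who have no major protocol violations". Section 9.2 confirms the hierarchy: "Analysis for all efficacy endpoints using the PP population will be the primary approach for analysis". The modified intention-to-treat (mITT) cohort is secondary.

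Section 9.1 gives the end of treatment visit no number or week. The rest of the protocol points to Week 64:

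- Section 6.5, headed End of Treatment / Study, contains one visit: "Visit 23: End of study visit Week 64/ Day 448".
- Section 6.4 runs the treatment period to Week 64 and says "The study treatment period will be for 52 weeks".
- Section 9.6 places the complete analysis at the end of the treatment period, as a separate step from the Week 36 analysis.

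The efficacy question closes much earlier:

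- The first co-primary endpoint in 9.4.1 is "Mean absolute change in haemoglobin level from baseline to 6 months after treatment with EPIAO/EPREX in parallel groups (g/dl"). The second, weekly dose per kg, has the same 6-month horizon.
- A secondary endpoint in 9.4.2 covers the "last 4 weeks of the period for assessment of treatment efficacy and safety (Weeks 32-36").
- Section 3.1.5 gives the second half of treatment another purpose: "treatment duration of 26 weeks for immunogenicity evaluation (weeks 40 through weeks 64").
- Section 9.6 says "This interim analysis will be conducted after all the randomized patients complete the Visit 16 (Week 36/Day 252"), and that the methods are those of the final analysis in section 9. The resulting report is intended to support local registration.

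**The concern.** Membership of the primary analysis set is settled up to 28 weeks after the endpoint has been measured. That causes two separate problems.

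**Selection on later events.** A subject who has both 6-month measurements but withdraws before Week 64 is removed from the primary comparison and survives only in the secondary mITT analysis. Some reasons for leaving may be related to treatment: section 3.1.6 makes withdrawal mandatory for anti-epoetin antibodies and for a dose need above 300 IU/kg/week, and the latter bears directly on the dose co-primary endpoint. In an equivalence trial, removing such subjects could make the arms look more alike than they are.

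**A set that does not yet exist.** The Week 36 analysis must follow section 9, and section 9 makes PP primary. A subject who has just completed Visit 16 cannot have completed Visit 23. Either the primary set at that analysis holds only the early-randomized subjects, or someone devises a different PP rule when the treatment codes are already open to the independent statistician. In both cases the interim and final primary results for the same endpoint rest on different sets.

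**Working it through.** **Timing.** Visit 8 is Day 91, Visit 16 is Day 252 and Visit 23 is Day 448 (6.3 to 6.5).

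- Visit 8 to Visit 16: (252 − 91)/7 = 23 weeks.
- Visit 8 to Visit 23: (448 − 91)/7 = 51 weeks.
- Visit 16 to Visit 23: 51 − 23 = 28 weeks.

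**The plan's own sample size (9.8).** 112 per group, about 18% drop-out, 132 per group randomized. 112 × 1.18 = 132.2 reproduces 132. Dividing instead gives 112/0.82 = 136.6, or 137. With 18% lost, 132 × 0.82 = 108 remain, already below 112. That shortfall comes from the inflation method and not from the PP rule; what the rule causes is the contrast between the counts at Visit 16 and Visit 23.

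**Subjects with Visit 16 data whom the Week 64 condition excludes.** The protocol does not say when the 18% is reached, so several cases are shown. Major violations are ignored throughout.

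| Assumption | Calculation | Excluded of 264 | Per group at Visit 16 / Visit 23 |
|---|---|---|---|
| 18% by Week 64, linear | 18% × 28/51 = 9.9% | 26 | 132 × (1 − 0.18 × 23/51) = 121 / 108 |
| 18% by Week 64, constant rate | 0.82^(23/51) − 0.82 = 9.4% | 25 | 121 / 108 |
| 18% by Week 64, three quarters of it before Visit 16 | 18% × 1/4 = 4.5% | 12 | 114 / 108 |
| 18% by Visit 16, same rate afterwards | 0.82 − 0.82^(51/23) = 17.6% | 46 | 108 / 85 |

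**Power, illustration only.** The protocol gives neither an SD nor an assumed true difference. I took a true difference of 0 and equivalence shown by a 95% confidence interval inside the margin (two one-sided tests at 2.5%, t-based), and chose the SD so that 112 per group gives a set power per endpoint. The normal approximation is 2Φ(margin/(SD√(2/n)) − 1.96) − 1.

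- 112 gives 80%: SD/margin = 2.30, that is 2.30 × 0.5 = 1.15 g/dl or 2.30 × 45 = 103.5 IU/kg/week. Power is 77.9% at 108 per group and 84.2% at 121. The normal approximation gives 78.0% and 84.0%.
- 112 gives 90%: SD/margin = 2.07. Power is 88.6% at 108 and 92.6% at 121.

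At 25 to 26 excluded, the Week 64 condition therefore costs about 4 to 6 percentage points per endpoint.

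**Week 36 analysis.** Suppose subjects are randomized uniformly over R weeks and the analysis is triggered when the last one completes Visit 16. Anyone randomized in the final 28 weeks of accrual cannot yet be at Week 64, so the share is min(1, 28/R):

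- R of 28 or less: 100%.
- R = 52: 28/52 = 54%, or 142 of 264.
- R = 78: 28/78 = 36%.
- R = 104: 28/104 = 27%, or 71 of 264.

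That such subjects exist needs no assumption about SD or drop-out. The last subject to complete Visit 16 is always one of them.

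**The case against.** The best defence is that Week 64 is an inference. Section 9.1 gives no visit number, and elsewhere the protocol calls Visit 23 the end of study visit. Sections 3.1.5, 9.4.2 and 9.6 suggest that efficacy was meant to close at about 6 months, so end of treatment in an efficacy set could mean the end of that block, and both problems would vanish. That may well be the intention, but no 6-month visit carries the name, while the heading of 6.5, the 52-week treatment period and the timing of the complete analysis all point to Week 64. If 6 months was meant, 9.1 still needs correcting.

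It can also be said that details of analysis sets belong in the SAP. Section 9.1 defers only the description of protocol violations to it; the visit criterion is fixed in the protocol.

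Section 4.2.2 asks for the last scheduled assessments when a subject withdraws, but does not say that this counts as completing the end of treatment visit. The mITT analysis does retain these subjects' data, which limits the damage but leaves the primary analysis as it is.

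Two points stand. No differential loss between the arms is shown, and no antibody sample is scheduled between Visit 16 and Visit 23, so bias is possible and not demonstrated. The counts and power figures also rest on inputs that the protocol does not give.

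**Conclusion.** The concern holds, and the protocol should be corrected. Followed as written, it removes subjects with complete 6-month data from the primary analysis because of events up to 28 weeks later, and it leaves the primary set of the registration analysis unformable for anyone who has not reached Week 64. Both conclusions follow from the text and the visit schedule, with the end of treatment visit read as Visit 23.

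The size is uncertain: 12 to 46 of 264 excluded, depending on the horizon and shape of the drop-out, and 27% to 100% not yet at Week 64 at the interim for accrual between 104 and 28 weeks. The loss of power is moderate. The more serious matters are that membership depends on events after the endpoint and that the interim and final sets differ. The secondary mITT analysis and the fact that the data are collected anyway keep this below a fatal flaw.

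**What to change.** In 9.1, define the PP set for the two co-primary endpoints as randomized subjects who completed baseline (Visit 8) and the named 6-month assessment visit, with no major protocol violation up to that visit. Name Visit 16 (Week 36), which already triggers the analysis in 9.6.

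Reconcile that choice with the other statements of the horizon: Visit 16 is 23 weeks after Visit 8 by the visit days, 9.6 speaks of 24 weeks, and 3.1.5 gives 26 weeks to Week 39, where no visit is scheduled.

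In 9.6, add that the same PP set serves the co-primary endpoints in the interim and final reports. If completion to Week 64 is wanted for the 52-week secondary endpoints, keep it as a separate, separately named set.

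The cost is wording in 9.1, a cross-reference in 9.6 and the reconciliation above, with no added patients, visits or models. The one drawback is having two PP definitions if the Week 64 set is kept.

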9.2 General Statistical Considerations

Analysis for all efficacy endpoints using the PP population will be the primary approach for analysis. Secondary analysis will be performed using the mITT population. For safety endpoints using the safety cohort will be the primary approach for analysis.

The SAS® package (SAS® Institute Inc., USA, and Version 9.2 or higher) will be used for statistical evaluation.

Descriptive statistics, such as mean, standard deviation, median, minimum and maximum values will be provided for the continuous variables and the number of observations and percentage will be provided for the categorical variables.

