4.2 Removal of Subjects from Therapy

4.2.1 Reasons for Withdrawal/Early Discontinuation

Any subject, who discontinues from the study treatment for any reason, will have his/her study treatment discontinuation recorded.

Subjects withdrawn prior to randomization but after signing informed consent:

- Screen Failure
- Withdrawal by Subject
- Investigator Decision

Subjects withdrawn after randomization but before completing the study as per protocol:

- Adverse Event as per PI discretion

- If subjects develop anti-epoetin antibodies or PRCA or severe allergic reaction
- If the subject requires epoetin dose more than 300 IU/kg/week
- Death
- Lost to Follow-up
- Pregnancy
- Progressive Disease
- Study Terminated by Sponsor
- Withdrawal by Subject

If a subject withdraws from the study, the investigator will complete and report the observations as thoroughly as possible up to the date of withdrawal including the date of last treatment and the reason for withdrawal.

If the subject is withdrawn due to an adverse event, the investigator will follow the subject until the adverse event has resolved or stabilized.

All subjects who are withdrawn from the study, effort should be made to complete protocol specified withdrawal procedures (Section 4.2.2).

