These tests will be performed during screening visit.

Urinalysis:

- Colour
- Transparency
- pH
- Specific gravity
- Protein
- Glucose
- Ketone bodies
- Bilirubin
- Blood
- Nitrite
- Urobilinogen
- Microscopic examination

These tests will be performed during screening and end of the study visit 23 (week 64/ Day 448).

Serum Beta HCG at screening, baseline visit (visit 8/Week 13/Day 91) and end of study visit 23 (week 64/Day 448)

Immunogenicity assessments

- Anti- epoetin Antibody by Radio Immunoprecipitation (RIP) Assay

For determination of anti-epoetin antibodies in human serum samples a RIP-assay will be employed. Serum samples for immunogenicity assessments will be collected at screening, baseline visit (visit 8/Week 13/Day 91), visit 5 (week 8/Day 56), visit 11 (week 16/Day 112), visit 13 (week 24/Day 168), visit 16 (week 36/ Day 252) and visit 23 (week 64/ Day 448).

The samples will be frozen at -80° C (for long term storage) or -20° C (for storage of 3 – 4 months) and kept until analysis in a central laboratory. In all patients, the last available blood sample will be analysed first. The last available sample for the interim analysis will be visit 16 (week 36) and for the end of the study analysis will be visit 23 (week 64/Day 448). Only if anti-epoetin antibodies are detected, all previous blood samples for the respective patient will be analysed in order to detect the time point of first occurrence.

The blood samples from the Russian centers will be shipped to the Laboratory at Chulalongkorn hospital. Blood samples of subjects who test positive for anti-epoetin antibody will be retained for lifelong years while the negative samples will be retained for one year from testing.

Apart from the above-mentioned visits, if the any of the following develop suggestive of possible antibody-mediated PRCA, the investigator can test for anti-epoetin antibody. A positive antibody test will be confirmed by bone marrow biopsy to rule of the incidence of PRCA.

- Sudden rapid decrease in haemoglobin concentration at the rate of 0.5 to 1.0 g/dl OR requirement of transfusions at the rate of approximately 1 to 2 per week, AND
- Normal platelet and white cell counts, AND
- Absolute reticulocyte counts less than 10,000/ μ L. This test will be performed with every visit when the CBC was done

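### The lead count of blood transfusions is taken in per-protocol completers, so subjects transfused and then withdrawn are counted only in the secondary mITT analysis

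*Protocol*

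**What the plan says.** Protocol section 9.1 makes PP the lead set for efficacy ("Per-Protocol cohort population will be considered as primary population for analysis of efficacy"), and section 9.2 extends this to every efficacy endpoint: "Analysis for all efficacy endpoints using the PP population will be the primary approach for analysis". No endpoint is exempted. mITT is named as the set for secondary analysis. The safety cohort, which is all randomised subjects, leads only for safety endpoints.

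PP membership depends on completion. Section 9.1 admits "All randomized subjects who complete both the baseline visit and end of treatment visit and who have no major protocol violations". Section 6.5, which covers the end of treatment and of the study, places that visit at Week 64 ("Visit 23: End of study visit Week 64/ Day 448").

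Section 9.4.2 lists "Incidence of blood transfusions" among the secondary efficacy analyses. Sections 3.1.3 and 7 also class it as efficacy, and it is on neither safety endpoint list (3.1.3, 9.5). The planned analysis is descriptive.

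Among the reasons for withdrawal after randomisation, section 4.2.1 includes "If subjects develop anti-epoetin antibodies or PRCA or severe allergic reaction" and a dose need above 300 IU/kg/week. Section 3.1.6 makes withdrawal from therapy mandatory on the same grounds. Section 4.2.3 classes those who do not complete as dropouts.

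**The concern.** A transfusion can be a sign of lost response, and lost response can end in withdrawal. A count restricted to subjects who reached Week 64 depends on something that happens after the event and may be related to it. If one arm has more subjects who lose response, are transfused and then leave, the PP table can show the arms as alike.

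The usual reason for leading with PP in an equivalence trial is that dilution in a full set may favour a finding of no difference against a margin. That reason applies to the two co-primary mean changes in section 9.4.1. It does not apply to an event percentage with no margin and no test.

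What is at stake is the headline transfusion figure in the report. Section 9.6 says that the interim analysis follows section 9 and that its report will support registration, so the ranking of the analysis sets carries into that report too. How the completer rule would apply at Visit 16 is not stated.

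**Working it through.** The protocol states no transfusion rate, so there is no figure to reproduce. The check traces the rules and then sizes the excluded group.

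**Tracing three hypothetical subjects through the rules**

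| Subject | PP (lead) | mITT (secondary) |
|---|---|---|
| Transfused, develops PRCA, withdrawn at Week 30 | not counted | counted |
| Transfused, needs more than 300 IU/kg/week, withdrawn | not counted | counted |
| Transfused once at Week 20, completes Week 64, no major violation | counted | counted |

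The mITT column assumes that each subject received study medication and has a baseline and at least one post-treatment measurement (section 9.1). Section 4.2.2 asks that withdrawn subjects complete the last scheduled assessments, but nothing says that this counts as the end of treatment visit. Sections 4.2.1 and 4.2.3 treat these subjects as not having completed.

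**Size of the excluded group** (section 9.8: 132 per arm, about 18% drop-out)

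- Outside PP through drop-out: 132 × 0.18 = 23.8, about 24 per arm.
- Remaining: 132 × 0.82 = 108.2, about 108 per arm, before any exclusion for major violations.

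**What this could do to the incidence (assumed rates)**

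Assume that 5% of completers are transfused and let d be the proportion of dropouts with a recorded transfusion. Incidence in all subjects = 0.82 × 5% + 0.18 × d, while PP reports 5.0% throughout.

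| d | All subjects | PP relative to all subjects |
|---|---|---|
| 0% | 4.1% | overstates by 0.9 points |
| 5% | 5.0% | no difference |
| 10% | 5.9% | understates by 0.9 points (0.9/5.9 = 15%) |
| 20% | 7.7% | understates by 2.7 points (2.7/7.7 = 35%) |
| 30% | 9.5% | understates by 4.5 points (4.5/9.5 = 47%) |

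The sign depends on whether d is above or below the completer rate, and the protocol does not settle that.

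**What this could do to the comparison (assumed counts)**

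Suppose that the arms have equal drop-out and equal numbers of transfused completers. Suppose also that one arm has k more subjects who are transfused and then withdrawn. PP shows a difference of 0. With 132 per arm as denominator the difference is k/132:

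- k = 1: 0.8 points
- k = 3: 2.3 points
- k = 5: 3.8 points
- k = 10: 7.6 points

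**The case against.** The strongest reply is that little is lost. Each point below stands to some degree.

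- **The events are not lost to the trial.** A reader might infer that transfused subjects who withdraw disappear from the analysis. They do not: the mITT analysis in section 9.2 would normally include them. Antibody-positive subjects, PRCA cases and withdrawals for adverse events are also reported under section 9.5, for which the safety cohort leads. Subjects withdrawn only for the dose cap are less clearly covered there, but mITT still holds them.
- **Transfusion is not a withdrawal reason.** A reader might infer from section 8.5 that it is. There, "requirement of transfusions at the rate of approximately 1 to 2 per week" is an alternative to a rapid haemoglobin fall. It prompts antibody testing only together with normal platelet and white cell counts and a low reticulocyte count, and treatment may restart after a negative result. The path to withdrawal runs through antibodies, PRCA, the dose cap or another listed reason.
- **The PRCA path is expected to be rare.** Section 1.3 calls antibody-induced PRCA very rare and seen predominantly with subcutaneous use, whereas this trial is intravenous. Subjects who need more than 300 IU/kg/week are excluded at screening.
- **The direction is not established.** A reader might infer a downward bias in each arm. The 18% covers drop-out in general, and the reasons in section 4.2.1 include loss to follow-up and withdrawal by the subject. Those who leave early also have less time in which a transfusion can be recorded, so PP could overstate incidence.
- **No decision rests on the endpoint.** It has no test and no margin.

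One reply does not stand, namely that the choice of set is left to the SAP. Section 9.2 fixes the lead set for all efficacy endpoints. For the analysis sets, section 9.1 defers only the detailed definition of a protocol violation.

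**Conclusion.** The point holds in a limited form. The protocol leads the transfusion count with a set defined by later completion and ranks second the set that would keep withdrawn subjects. That is a poor choice for an event that can precede withdrawal, and the equivalence rationale for PP does not justify it here.

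The lead result would leave out about 24 subjects per arm at the planned drop-out. Whether that understates incidence, overstates it or hides an arm difference depends on transfusion rates that the protocol does not give. The percentages in the working are illustrations under assumed rates and should not be cited as an expected bias.

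A reader might also infer that the trial's main conclusion is at risk from this endpoint. It is not: equivalence rests on the haemoglobin and dose comparisons in section 9.4.1. This is a minor improvement to a descriptive secondary endpoint.

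**What to change.** In section 9.2, with a matching line in 9.4.2, exempt transfusion incidence from the PP-first rule:

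- **Main set:** all randomised subjects who received at least one post-randomisation dose, analysed by arm. This is close to the existing mITT and safety cohorts. The dose should be specified as post-randomisation because every subject receives EPREX during titration.
- **Count:** subjects with at least one transfusion from the first randomised dose to end of treatment or withdrawal, whichever comes first.
- **Supportive:** the same count in PP.

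The cost is one sentence and at most one extra descriptive table. No new data are needed, since section 4.2.1 already requires observations to be reported up to the date of withdrawal. No clinical rule changes. The one downside for the sponsor is that the headline incidence may be slightly less favourable.
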